^f A 12-lead ECG will be measured at V1, V2 and V4 or Early Termination before the spirometry, bronchodilator, run-in ICS medication (QVAR[®]) or study drug intake.

^g One commercial albuterol HFA MDI (200 actuations) will be prescribed and supplied by the investigator to each subject at V1, and resupplied as needed At V2-3 based on assessment of doses used between visits.

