7.2.10 Blood Hematology and Chemistry

Blood samples of approximately 12 mL will be collected for hematology and serum chemistry at Visit 1 (screening), Visit 4 and Early Termination in the morning, after an overnight fasting of at least 10 hours (only water is allowed during the night). At V1, the blood draw should be performed after vital signs and 12-lead ECG recording, but before administration of albuterol and background

QVAR®. An additional blood sample will be collected for serum pregnancy test in women of childbearing potential at visits 1 and 4 (including an early termination visit).

The following evaluations will be performed using a laboratory:

- A hematology test: red blood cells count (RBC), white blood cells count (WBC) and differential, total hemoglobin (Hb), hematocrit (Hct), and platelets count (PLT).
- A serum chemistry test: blood urea nitrogen (BUN), cholesterol, triglycerides, creatinine, uric acid, aspartate aminotransferase (AST), alanine aminotransferase (ALT), Gamma-glutamyl transpeptidase (γ -GT), total bilirubin, alkaline phosphatases, albumin, total proteins, and electrolytes (sodium, potassium, calcium, and chloride).
- Fasting blood glucose
- A serum pregnancy test (serum β -hCG) in women of child-bearing potential.

Blood collection and sample preparation will be performed according to procedures provided by the laboratory which will be in charge to transmit the results to the Investigator. In case of clinically significant abnormality, findings will be reported in the medical history (if occurred at V1), or as an Adverse Event (if occurred after V1).

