10.8 Early Termination and Unscheduled Visits

The handling of the early termination efficacy and safety assessments in the statistical analyses will be discussed during the Data Review Meeting and the decisions will be fully documented in the Data Review Report.

With regards to unscheduled assessments, will be evaluated case by case during the Data Review Meeting.

The following rules on data re-allocation will be considered:

- Data collected at multiple visits (spirometry, ACQ score, vital signs, laboratory data, and ECG) recorded at the study termination visit for discontinued patients will be re-allocated by selecting the next visit at which the assessment was planned. For each assessment, only the visits at which the assessment was scheduled will be considered for re-allocation. This means that ECG and laboratory data can be re-allocated only to Visit 4. For example, if the last visit performed before the study termination visit was Visit 2, the data recorded at the study termination visit will be re-allocated to Visit 3 for spirometry, ACQ score, and vital signs, and to Visit 4 for 12-lead ECG and laboratory data. If the study termination visit was performed less than 7 days after the preceding visit, then the data recorded at the study termination visit will not be re-allocated and they will be excluded from the statistical analysis.
- For discontinued patients, efficacy data recorded in the diaries from the last visit performed before the study termination visit or the date of discontinuation onwards will be reallocated to the next expected inter-visit period;
- in case of missing intermediate visit not due to the re-allocation of data collected at the study termination visit (e.g., Visit 3 missing, but Visits 2 and 4 performed), an expected date for the missing Visit 3 will be imputed in order to define the inter-visit periods for diary data. The expected date for the missing Visit 3 will be imputed as follows: Visit 3 expected date = Visit 2 date + 28 days.
- Additional unscheduled/optional assessments will be considered on a case-by-case basis and their inclusion in the analysis will be discussed at the DRM and confirmed in the DRR prior to data base lock and unblinding.

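### The SAP's 7-day rule for termination visits also removes ECG, laboratory and vital-sign values from the safety tables; for ECG and laboratory tests these are the subject's only scheduled on-treatment values

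*SAP*

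**What the plan says.** SAP 10.8 sets one re-allocation rule for "Data collected at multiple visits (spirometry, ACQ score, vital signs, laboratory data, and ECG") recorded at a discontinued subject's termination visit. Each item moves to the next visit at which it was planned, and the SAP draws the consequence that "ECG and laboratory data can be re-allocated only to Visit 4". An exception follows. "If the study termination visit was performed less than 7 days after the preceding visit", the data "will not be re-allocated and they will be excluded from the statistical analysis". The exception names no assessment and does not separate efficacy from safety.

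The schedules differ by assessment. Protocol 7.1, in a footnote to the flow diagram, states: "A 12-lead ECG will be measured at V1, V2 and V4 or Early Termination before the spirometry". Protocol 7.2.10 states that blood "will be collected for hematology and serum chemistry at Visit 1 (screening), Visit 4 and Early Termination". Blood pressure is taken at every clinic visit from Visit 1 to Visit 4 and at early termination.

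Protocol 12.3.6 plans laboratory shift tables that run from the screening value to the end-of-treatment value, and QTcF threshold counts at the post-baseline visit. SAP 10.7.3.1 and 10.7.4 tabulate ECG and laboratory shifts at Day 1 and Week 8 only. SAP 3.8 reports no change from the protocol.

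**The concern.** A minimum spacing can be defended for efficacy: a spirometry value taken a few days after Visit 2 or Visit 3 says little about Week 4 or Week 8. Safety summaries have another purpose. They should show what was measured while subjects were exposed, including subjects who stopped.

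For ECG and laboratory tests the clock can also run from a visit that has no bearing on them. Visit 3 includes neither, so a recent Visit 3 does not make the termination value redundant. Because the SAP tables have only Day 1 and Week 8 columns, an excluded termination value has no other way into the by-arm QTcF counts, ECG changes or laboratory shifts. Outlier counts of this kind can be small, so one omitted subject could change what an arm shows.

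**Working it through.** **Does the rule as written reach safety data?** Yes. Vital signs, laboratory data and ECG are named in the rule, and the exclusion covers whatever was recorded at the termination visit. The re-allocation sentence is tailored to each assessment; the exclusion sentence is not. It refers to the preceding visit, not to the preceding visit with that assessment.

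**What is lost, by timing of the termination visit:**

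| Termination visit | ECG | Laboratory | Blood pressure |
|---|---|---|---|
| 1–6 days after Visit 2 | Excluded. The Visit 2 ECG is the pre-dose baseline, so no on-treatment value remains | Excluded. The last scheduled test was at Visit 1, so none remains | Excluded. Visit 2 is the pre-dose baseline, so none remains |
| 7 or more days after Visit 2, before Visit 3 | Kept as Visit 4 (Week 8) | Kept as Visit 4 (Week 8) | Kept as Visit 3 |
| 1–6 days after Visit 3 | Excluded. Not done at Visit 3, so none remains | Excluded. Not done at Visit 3, so none remains | Excluded, but the Visit 3 value remains |
| 7 or more days after Visit 3 | Kept as Visit 4 (Week 8) | Kept as Visit 4 (Week 8) | Kept as Visit 4 (Week 8) |

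**Exposure in the third row.** Visit 3 is 28 ± 2 days after Visit 2, that is, 26 to 30 days. Adding 1 to 6 days gives 27 to 36 days after Visit 2.

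**Internal consistency.** With Visit 3 on day 28, an ECG or blood test from a termination visit 7 days after Visit 2 is analysed as Week 8, while one from day 34 (28 + 6) is dropped. Avoiding short exposure cannot explain this, since the longer exposure is the one discarded. Avoiding duplicate values cannot explain it either, since Visit 3 has no ECG or blood test.

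**Consistency with the protocol.** When a termination visit takes place, SAP 7.1 takes its date as the end of the randomized treatment period. In the SAP's own terms, a value from that visit is therefore an end-of-treatment value, which is what the protocol's shift tables call for.

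**How many subjects?** The rule rests on no stated figure, and the documents give no withdrawal timing. The only usable plan figures are from Protocol 12.1. They reproduce: 99 / (1 − 0.15) = 116.5, rounded up to 117 per group, and 5 × 117 = 585 randomized for 495 evaluable. The difference is 585 − 495 = 90.

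Taking all 90 as withdrawals with a termination visit (an assumption):

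- Even spread over days 1 to 55 after Visit 2, leaving out day 28: the two windows hold 6 + 6 = 12 of 54 days, or 22%. 90 × 12/54 = 20 subjects, or 4 per arm.
- 10% in the windows: 90 × 0.10 = 9 subjects.
- 40% in the windows: 90 × 0.40 = 36 subjects.

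The sample size and the primary test play no part in this point.

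**The case against.** The strongest reply is that little is truly lost and nothing is final. SAP 10.8 leaves the handling of early-termination assessments to the Data Review Meeting and provides for problems with the rule to be looked at during blind review. SAP 10.7.4 lists all laboratory data with abnormal values flagged, and SAP 11 plans all-randomized listings for vital signs, ECG results and prolonged QTcF. Clinically significant ECG and laboratory findings are reported as adverse events (Protocol 7.2.5, 7.2.10 and 10.8). Adverse-event tables go by onset date with no spacing rule, and the subject stays in the Safety population. All of this stands, and it lowers the stakes. It does not put the values into the by-arm counts and shift tables, and blind review would be correcting a default that could be written correctly now.

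A reader might infer more than the documents support:

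- That early withdrawals in general lose their safety data. Only termination visits less than 7 days after Visit 2 or Visit 3 are affected.
- That the clock always runs from a visit without the assessment. ECG is done at Visit 2, although only as the pre-dose baseline; for ECG this holds only after Visit 3.
- That vital signs are affected in the same way. After Visit 3 an on-treatment blood pressure remains in the tables.
- That abnormal values are hidden. They leave the tables, not the report.
- That those affected mostly stopped for safety reasons. Protocol 4.4 lists several reasons for withdrawal and gives no frequencies.

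**Conclusion.** The point holds in a limited form. As written, the rule removes from the safety tables the only scheduled on-treatment ECG and laboratory values of any subject whose termination visit falls 1 to 6 days after Visit 2 or Visit 3, and the only on-treatment blood pressure when it falls 1 to 6 days after Visit 2. This conflicts with Protocol 12.3.6 and treats longer exposure worse than shorter exposure. That conclusion follows from the text and needs no assumption about numbers.

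The size is unknown. The range of 9 to 36 subjects assumes 90 withdrawals, a termination visit for each, and 10% to 40% of them in the two windows. Non-evaluable is not the same as withdrawn, and Protocol 7.1.7 promises only best efforts to hold the visit, so neither the range nor the even-spread figure of 20 is a forecast. The affected tables are descriptive. The change is worth making before unblinding because the written default is wrong and easy to correct.

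**What to change.** In SAP 10.8, limit the less-than-7-days exclusion to spirometry and ACQ. For ECG, laboratory tests and vital signs, include every on-treatment termination value in an end-of-treatment row, defined as the last post-baseline value, in the summary, QTcF-threshold and shift tables. Keep that row separate from the nominal Week 8 row, and align SAP 10.7.2, 10.7.3.1 and 10.7.4 with it.

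Two simpler repairs fall short. Running the 7-day clock from the last visit with the same assessment would still drop an ECG or blood pressure taken within 6 days of Visit 2. Sending every termination value to the next scheduled visit would label an ECG from the first days of treatment as Week 8.

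The cost is a short change to the SAP text and one extra row in existing tables. No new data are needed and the primary analysis is unaffected. The small downside is that some end-of-treatment values will reflect short exposure; these should be flagged.
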